8.1. Subject Disposition

Subject disposition will be provided for all subjects screened. A summary table will present the total number of subjects screened, total number of screen failures, and total number who received any study drug. Among subjects who received any study drug, this summary will also present the frequency and percentage of subjects who completed treatment, and who discontinued treatment. The primary reasons for discontinuation of treatment, and for end of study will be tabulated.

Detailed subject disposition information, as well as eligibility and analysis population assignment will provided in listings.

8.2. Protocol Violations

The frequency and percentage of subjects discontinued due to protocol violation will be summarized in the disposition table described above.

Protocol violations resulting in early termination of subjects will be presented in the disposition listing.

8.3. Demographics and Baseline Characteristics

Descriptive statistics of demographic measurements at screening such as age, sex, ethnicity, race, measurements of height and weight, number of prior transfusions, and Eastern Cooperative Oncology Group Performance Status (ECOG) performance status score at Screening will be summarized for the ASaT Population and for the FAS population..

Medical and surgical history / physical findings will be coded using latest Medical Dictionary for Regulatory Activities (MedDRA) version and summarized by system organ class (SOC)/ preferred term (PT) for the ASaT Population.

A summary of MDS diagnosis at screening will be provided for the ASaT population.

The response to previous anti-cancer therapies will be summarized for both the ASaT population, and the FAS population.

Data for demographics and baseline characteristics will be presented in listings.

8.4. Dosing and Extent of Exposure

Average compliance will be calculated for each subject as the average over all daily reported values of (actual dose / planned dose) $\times 100\%$.

Number of treatment cycles and average compliance will be summarized using descriptive statistics. Frequency and percentage of subjects who experienced total incidences of drug modification (dose reduction, dose interruption, dose increase, or drug withdrawn) will be summarized.

Data for study drug dispensing and dosing will be presented in listings.

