9.2 Treatment Administration

Tipifarnib will be administered orally, with food to each subject according to one of the following dose regimens:

- Regimen 1: 600 mg bid for 7 days on Days 1-7 in 28 day cycles (i.e. 1 week on / 3 weeks off).
- Regimen 2: 300 mg bid for 21 days on Days 1-21 in 28 day cycles (i.e. 3 weeks on / 1 week off).

On Day 1 of Cycle 1, only 1 dose of tipifarnib will be administered and will take place in the evening. Thereafter, tipifarnib will be administered orally with a meal in the mornings and again approximately 12 hours later, at approximately the same times each treatment day. Tablets should be swallowed whole with water (~8 oz. or 250 mL), but may be chewed or crushed if the Investigator deems it necessary.

Subjects may use proton pump inhibitors or H2 antagonists during the treatment portion of this study. However, subjects should be instructed to use antacids (magnesium or aluminum containing products) at least 2 hours before or after intake of oral study drug.

On Cycle 1 Day 1, the study site will provide tipifarnib to the subject from bulk supplies. Subjects will be provided with diaries with instructions to record the date and time of each dose and asked to bring the diaries and tablet bottles to each clinic visit for subject compliance and drug accountability review by the site staff.

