9.8 Treatment Compliance

The importance of treatment compliance should be emphasized to the subject. Subjects will be given study drug and detailed instructions on how to take medications at home. Subjects will be instructed to return all used and unused study drug containers at each study visit. Subject compliance with the dosing schedule will be assessed by reconciliation of the used and unused study drug at each clinic visit and review of the dosing diaries. The quantity dispensed, returned, used, lost, etc. must be recorded on the dispensing log provided.

Compliance will be monitored and documented by site personnel on the appropriate form. The site personnel will question the subject regarding adherence to the dosing schedule by reviewing the dosing diaries, recording the number of tablets (and strengths, if applicable) returned, the date returned, and determining treatment compliance (at least 80% of the total assigned dose) before dispensing new medication to the study subject.

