6. ANALYSIS POPULATIONS

Full Analysis Set (FAS)

The full analysis set (FAS) will serve as the primary population for the analysis of ORR and other efficacy-related data. Prior to Protocol Amendment 3 (version 09 Jul 2017), other subjects were enrolled into the trial using a different dose regimen. Also, for inclusion in the FAS, subjects must meet all Protocol Amendment 3 inclusion criteria. For the purposes of the primary analysis (advancement from stage 1 to stage 2 and overall analysis for each dose regimen

cohort), those subjects will not be included. The excluded subject data will be summarized separately in the reporting of the study.

Therefore, subjects will be excluded for FAS for the following reasons:

- Did not meet eligibility criteria as outlined in Protocol Amendment 3 (version 09 Jul 2017)
- Failure to receive at least one dose of tipifarnib
- No post-baseline endpoint data subsequent to at least 1 dose of study drug.
- Enrolled prior to Protocol Amendment 3 (version 09 Jul 2017)

Per-Protocol (PP) Population

A supportive analysis may be performed on the PP population which excludes subjects due to important deviations from the protocol that may substantially affect the results of the primary analysis, such as not taking at least 80% of the intended dose in cycle 1. The final determination on protocol violations, and thereby the composition of the PP population, will be made prior to locking the clinical database and final analysis and will be documented in a separate memorandum.

All Subjects as Treated (ASaT) Population

The ASaT population will be used for the analysis of safety data. The ASaT population consists of all enrolled subjects who receive at least one dose of tipifarnib. At least one laboratory or vital sign measurement obtained subsequent to at least one dose of study drug is required for inclusion in the analysis of a specific safety parameter. To assess change from baseline, a baseline measurement is also required.

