7.5. Handling of Dropouts or Missing Data

Where individual data points are missing because of insufficient samples, dropouts, or other reasons, the data will be analyzed based on reduced denominators. For survival analysis, dropouts without confirming events will be treated as censored.

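### SAP 8.4 averages compliance over reported days only, so dosing days that are both untaken and unrecorded drop out and compliance is overstated

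*SAP*

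**What the plan says.** SAP 8.4 gives one compliance formula: "Average compliance will be calculated for each subject as the average over all daily reported values", each value being actual dose over planned dose, times 100%. It is not restricted to any cycle and has no rule for a dosing day without a value. Its stated use is a summary: "Number of treatment cycles and average compliance will be summarized using descriptive statistics".

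SAP 13 refers missing-data conventions to the section for each endpoint. SAP 8.4 contains none, which leaves the general rule in SAP 7.5, that "the data will be analyzed based on reduced denominators".

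Two other places use an 80% dose threshold:

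- Protocol 9.8 has site staff reconcile used and unused drug and review the diaries, with the task of "determining treatment compliance (at least 80% of the total assigned dose") before new drug is dispensed.
- SAP 6 and Protocol 12.1.1 define the per-protocol population by excluding important deviations, "such as not taking at least 80% of the intended dose in cycle 1". Membership is settled before database lock and recorded in a memorandum. The analysis is supportive and optional.

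SAP 15 lists no change from the protocol's statistical methods.

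**The concern.** A mean over reported values conditions on a record existing. Dosing days with no entry are plausibly those on which the dose was missed. If they are, they leave both numerator and denominator, and the average describes only the days on which the subject was dosing and recording.

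Compliance is a planned reported result, and Protocol 9.4 says the study's data will be used to choose a dose and regimen. The error per blank day also differs between regimens, because cycle 1 has 7 dosing days in Regimen 1 and 21 in Regimen 2. An overstated figure could make either schedule look better followed than it was.

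A second, smaller issue is that SAP 6 names an 80% threshold without giving a formula, a data source or a rule for unrecorded days. Someone programming that flag would find only the SAP 8.4 definition in the SAP.

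**Working it through.** The documents give no compliance result, and no stated sample size, error rate or power depends on the formula, so there is no plan figure to reproduce. The check is direct arithmetic for cycle 1.

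**Inputs.** Protocol 9.2 gives Regimen 1 as twice daily on Days 1–7 and Regimen 2 as twice daily on Days 1–21. It adds: "On Day 1 of Cycle 1, only 1 dose of tipifarnib will be administered". Planned cycle 1 doses are therefore:

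- Regimen 1: 1 + 6 × 2 = 13
- Regimen 2: 1 + 20 × 2 = 41

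**Three measures compared**

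- (a) SAP 8.4 with missed days blank: mean of actual/planned over reported days.
- (b) SAP 8.4 with missed days entered as 0: the same mean over all dosing days.
- (c) Total doses taken / total doses planned.

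**Full dosing at first, then nothing**

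| Case | (a) blank | (b) entered as 0 | (c) taken/planned |
|---|---|---|---|
| Regimen 1, Days 1–4 taken | 4/4 = 100% | 4/7 = 57.1% | 7/13 = 53.8% |
| Regimen 1, Days 1–5 taken | 5/5 = 100% | 5/7 = 71.4% | 9/13 = 69.2% |
| Regimen 2, Days 1–11 taken | 11/11 = 100% | 11/21 = 52.4% | 21/41 = 51.2% |
| Regimen 2, Days 1–16 taken | 16/16 = 100% | 16/21 = 76.2% | 31/41 = 75.6% |

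The distortion comes almost entirely from blanks. Once missed days are entered as 0, (b) and (c) differ by at most 3.3 percentage points in these cases.

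**Days needed to fall below 80% on (c).** In Regimen 1, one missed full day leaves 11/13 = 84.6% and two leave 9/13 = 69.2%. In Regimen 2, four leave 33/41 = 80.5% and five leave 31/41 = 75.6%. Measure (a) stays at 100% throughout if those days are blank.

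**Different periods.** Suppose every day is recorded, with 50% of dose in cycle 1, full dosing afterwards and equal weight per cycle. The all-cycle average is (0.5 + 2)/3 = 83.3% over three cycles and (0.5 + 5)/6 = 91.7% over six. An all-cycle average above 80% thus says nothing certain about cycle 1, even with complete records.

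**Day 1 weighting.** The single-dose first day counts as a full day in the daily mean. Missing only that day in Regimen 1 gives 6/7 = 85.7% under (b) and 12/13 = 92.3% under (c). The effect is small and here runs downward, so it is not part of the overstatement.

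**The case against.** A reader might infer that a subject who took half the dose would score 100% and so pass the 80% per-protocol cut. The documents do not support that. The criterion is worded as "not taking at least 80% of the intended dose in cycle 1", which is already dose taken over dose intended, in one cycle. At 53.8% and 51.2%, the example subjects fail it. Nothing links the criterion to the SAP 8.4 average. The criterion is also given only as an example, with membership decided before lock.

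Other points on that side:

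- **Source of the values.** SAP 8.4 does not say that its daily values come from diaries alone. Protocol 9.8 adds drug reconciliation and questioning of the subject. The case report form is not among the documents, so whether a missed day is left blank or entered as 0 is unknown. This stands: every 100% figure rests on blanks.
- **Protocol 9.8.** Its threshold is a site check before dispensing, not an analysis definition, so there is no clear contradiction with SAP 8.4. This stands too. Protocol 9.8 shows that a total-dose basis and the data for it already exist, and no more than that.
- **Impact.** Average compliance is only summarized. The FAS has no compliance criterion, and no decision rule or response estimate uses the average. SAP 8.4 also reports cycles, dose reductions, interruptions and withdrawals, with dosing listings. This stands and limits the point to a minor one.

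What remains is a formula that averages reported values only, has no rule for unrecorded dosing days, and falls back on reduced denominators.

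**Conclusion.** The point holds as a minor, inexpensive correction. As written, SAP 8.4 overstates compliance whenever a dosing day is both untaken and unrecorded. Under the assumption that missed days are blank, intake of 54% (Regimen 1) or 51% (Regimen 2) in cycle 1 is reported as 100%. If they are entered as 0, the formula gives 57.1% and 52.4%, and the problem nearly disappears. The documents do not show which applies.

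The point does not extend to the per-protocol population as defined. It does mean that the SAP 8.4 average should not be used for the 80% criterion, since it covers all cycles and can omit missed days. The primary FAS analysis and the two-stage decision rule do not depend on it.

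**What to change.** In SAP 8.4, define compliance as total dose taken / total dose planned × 100%, over all planned dosing days at the assigned dose level, per cycle and overall. Count Cycle 1 Day 1 as one planned dose. State that diary entries are reconciled with returned-tablet counts, as Protocol 9.8 already provides, and that an unrecorded dosing day counts as not taken unless the tablet count shows otherwise. In SAP 6, name the cycle 1 value of this measure as the one used for the 80% criterion.

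The cost is a change of wording and programming; diaries and tablet counts are already collected. Reported compliance may be slightly lower. It could be understated where doses were taken but not logged and the tablet count cannot settle the matter, so it would help to list the subjects with unresolved unrecorded days beside the summary.

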8.5. Concomitant Medications

Prior cancer therapies, and prior and concomitant medications (other than cancer treatment) will be coded by WHO Drug Dictionary (version December 2016) and summarized by preferred ATC3 terms and preferred terms.

Data for prior prior cancer therapies and for prior and concomitant medication (other than cancer treatment) will be presented in listings.

8.6. Follow Up Assessments

The dates of post treatment follow up assessments for subsequent therapy and for survival will be presented in listings.

9. EFFICACY ANALYSES

The efficacy of tipifarnib will be assessed based on the following endpoints:

- Response assessments according to the MDS IWG criteria (Table 8 and Table 9 in the study protocol).
- Transfusion requirements during the study period.

9.1. Primary Efficacy Analyses

The objective response rate will be estimated and includes the following response types CR, PR, marrow CR and HI according to the MDS IWG criteria (Table 8 and Table 9 in the study protocol). The estimate of the ORR will be calculated based on the maximum likelihood estimator (i.e., crude proportion of subjects whose best overall response is CR, PR, marrow CR or HI). The estimate of the ORR will be accompanied by a 2-sided 95% exact binomial confidence interval.

9.2. Secondary Efficacy Analyses

Transfusion independence and disease response will be summarized descriptively per dose regimen cohort and overall.

The duration of objective response will be calculated for subjects who achieve CR, PR, marrow CR or HI. For such subjects, the duration of objective response is defined as the number of days from the start date of response (whichever response is achieved first) to the first date that progressive disease(PD) is objectively documented. Disease progression will be determined by the Investigator using MDS IWG criteria (Table 9 in the study protocol). The DOR will be right-censored for subjects who achieve a response and meet 1 of the following conditions:

- 1) Non-protocol anticancer treatment started before documentation of disease progression;
- 2) Death or documented disease progression after more than 1 missed disease assessment visit;
- 3) Alive and does not have documentation of disease progression before a data analysis cutoff date.

The DOR will be summarized descriptively using the Kaplan-Meier method. The 50th percentile of the Kaplan-Meier distribution will be used to estimate the median response duration.

PFS will be defined as the time (in months) from enrollment to either first observation of progressive disease or occurrence of death due to any cause within 1 year (approximately 4 time intervals for disease assessments) of either first administration of tipifarnib or the last disease assessment. Similarly, survival will be defined as the time (in months) from enrollment to occurrence of death due to any cause within 1 year (approximately 4 time intervals for disease assessments) of either first administration of tipifarnib or the last disease assessment.

Determination of RBC transfusion independence will be assessed by the Investigator through the review of subject transfusion requirements and hemoglobin levels. RBC TI will be defined as the absence of the intravenous infusion of any RBC transfusion during any consecutive “rolling” 56 days during the treatment period, i.e. days 1 to 56, days 2 to 57, days 3 to 58, etc. and a ≥ 1 g/dL increase in hemoglobin level. The rise in the hemoglobin concentration in subjects who no longer require transfusions will be calculated as the difference between the maximum hemoglobin concentration and the minimum pre-transfusion value during the 12 weeks before enrollment in the study.

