Progression free survival will be defined as the time (in months) from enrollment to either first observation of progressive disease or occurrence of death due to any cause within 1 year (approximately 4 time intervals for disease assessments) of either first administration of tipifarnib or the last disease assessment. Similarly, survival will be defined as the time (in months) from enrollment to occurrence of death due to any cause within 1 year (approximately 4 time intervals for disease assessments) of either first administration of tipifarnib or the last disease assessment

Determination of RBC TI will be assessed by the Investigator through the review of subject transfusion requirements and hemoglobin levels. RBC TI will be defined as the absence of the intravenous infusion of any RBC transfusion during any consecutive "rolling" 56 days during the treatment period, i.e. days 1 to 56, days 2 to 57, days 3 to 58, etc. and a \geq 1 g/dL increase in hemoglobin level. The rise in the hemoglobin concentration in subjects who no longer require transfusions will be calculated as the difference between the maximum hemoglobin concentration and the minimum pre-transfusion value during the 12 weeks before enrollment in the study.

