14.2 Source Data and Subject Files

The Investigator must keep a subject file (medical file, original medical records) on paper or electronically for every subject included in the study. This file will contain the available demographic and medical information for the subject, and should be as complete as possible.

In particular, the following data should be available in this file:

- Subject's full name
- Date of birth
- Gender
- Height
- Weight
- Relevant medical history and concomitant diseases
- Prior and concomitant therapies (including changes during the study)
- Trial identification
- Date of subject's inclusion into the study (i.e. date of informed consent)
- Subject identifier in the study
- Dates of the subject's visits to the site
- Dates and number of RBC, whole blood and platelet transfusions
- Any medical examinations and clinical findings predefined in the clinical study protocol
- All AEs observed in the subject
- Date of subject's end of study, and
- Date of and reason for early withdrawal of the subject from the study or from treatment, if applicable.

It must be possible to identify each subject by using this subject file. Additionally, any other documents containing source data must be filed. This includes original printouts of data recorded or generated by automated instruments, bone marrow evaluation, laboratory value listings, etc.

Such documents must bear at least the subject identifier and the date when the procedure was performed. Information should be printed by the instrument used to perform the assessment or measurement, if possible. Information that cannot be printed by an automated instrument will be entered manually. Medical evaluation of such records should be documented as necessary and the documentation signed and dated by the Investigator.

The following information described in the CRFs is regarded as the source data:

- Any Investigator's comments
- Subject identifier
- Information on AEs (e.g. seriousness, severity, outcome, and causality to the IP)
- Reason for providing concomitant medications and procedures (if applicable)
- Assessment of disease response
- Description about study discontinuation

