3.2. Secondary Objectives and Endpoints

Secondary Objective 1: To assess the effect of tipifarnib on the following:

- Rate of Transfusion Independence

- Duration of Transfusion Independence
- Hematologic Improvement (HI)
- Duration of Response (DOR)
- Rate of progression free survival (PFS) at 1 year
- Rate of survival at 1 year
- Safety and tolerability

Secondary Endpoint 1: Response assessments according to the MDS IWG criteria (Table 8 and Table 9 in the study protocol); Transfusion requirements and hemoglobin levels during the study period; Adverse events (AE) and serious adverse events (SAE) evaluated according to the National Cancer Institute- Common Terminology Criteria for Adverse Events (NCI CTCAE) v.4.03.

Secondary Objective 2: To evaluate the activity of tipifarnib in subjects treated with two different tipifarnib dose regimens (regimen 1 and regimen 2).

Secondary Endpoint 2: Response assessments according to the MDS IWG criteria (Table 8 and Table 9 in the study protocol).

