Subjects who received a starting dose of 900 mg bid during the conduct of the original version of this protocol may be dose reduced to the 600 mg bid dose at the discretion of the investigator (protocol Amendment 1). Subjects who received tipifarnib on Days 1 – 7 and Days 15 – 21 during the conduct of the original version and amendment 1 of this protocol, may transition to

the new treatment administration schedule (tipifarnib on Days 1-7 in 28 day cycles) beginning on Day 1 of their next cycle.

Subjects accrued prior to Protocol Amendment 3, 09 July 2017, will not be included in the total disposition and were not considered in the sample size determination detailed in section 5 of this SAP. The estimated number of 36 subjects enrolled do not include these subjects. For analysis, this subject population will only be included in the Total Adverse Event tables.

In the absence of unmanageable toxicities, subjects may continue to receive tipifarnib treatment until disease progression. If a complete response (CR) is observed, therapy with tipifarnib will be maintained for at least 6 months beyond the start of response.

Hematologic assessments, including peripheral blood evaluations and review of transfusion requirements, will be performed at screening and at least monthly until disease progression. Disease assessments will also be performed at screening and at least once every approximately 12 weeks starting at the end of cycle 3. As part of the disease assessment at screening and during Cycles 3, 6 and 9, bone marrow evaluation will be performed. Thereafter, bone marrow evaluations will occur during disease assessments in accordance with institutional standard practice. Additional hematologic or disease assessments may be conducted if deemed necessary by the Investigator. The timing of the hematologic and disease assessments should be maintained as much as possible independently of potential treatment cycle delays.

Determination of ORR will be assessed by the Investigator according to the MDS International Working Group (IWG) criteria (Table 8 and Table 9 in the study protocol).

Upon disease progression, all subjects in the study will be followed approximately every 12 weeks for survival and the use of subsequent therapy until either death or 12 months after accrual of the study has been completed, whichever occurs first. Information on survival and subsequent anticancer therapy may be collected by phone.

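### Survival and PFS are defined through deaths within a year of the first dose or of the last disease assessment, with no governing anchor and no estimator, so the 1-year rates are not fixed

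*SAP*

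**What the plan says.** SAP 3.2 lists "Rate of survival at 1 year" as a secondary objective, next to the 1-year PFS rate. The only definition is in SAP 9.2: "survival will be defined as the time (in months) from enrollment to occurrence of death due to any cause within 1 year", where the year is counted from the date "of either first administration of tipifarnib or the last disease assessment". Protocol 12.2.1 has the same rule: "Similarly, survival will be defined as the time (in months) from enrollment to occurrence of death due to any cause within 1 year". In both documents the sentence follows the PFS definition, which uses the same two anchors.

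Three neighbouring provisions bear on how the rate would be computed:

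- **Estimator.** SAP 9.2 names one for duration of response ("The DOR will be summarized descriptively using the Kaplan-Meier method") but none for survival or PFS.
- **Censoring.** SAP 7.5 says: "For survival analysis, dropouts without confirming events will be treated as censored". It is silent on a recorded death that falls outside the window.
- **Follow-up.** SAP 4.1 follows subjects for survival after progression "until either death or 12 months after accrual of the study has been completed, whichever occurs first". Early enrollees are therefore followed well past their own month 12, whether or not disease assessments continue.

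SAP 15 reports no changes from the protocol's methods.

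**The concern.** A 1-year survival rate needs a time origin, all deaths, a censoring rule and an estimator. The plan instead gives a rule for which deaths count, and one of its two anchors moves with the visit schedule. Take month 0 as the first dose and allow either anchor:

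- Last assessment at month 12, death at month 20: counted (8 months after the assessment), although the subject lived past 1 year.
- Last assessment at month 3, death at month 14: counted (11 months after), although the subject lived past 1 year.
- Last assessment at month 3, death at month 16: not counted (13 months after the assessment, 16 after the dose).

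The first two cases would pull a crude 1-year rate down. The third does that rate no harm, but it shows that a recorded death is kept or dropped according to an unrelated visit date.

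A crude tabulation is a realistic reading. SAP 9.1 makes the plan's other rate, ORR, a crude proportion. SAP 13 summarises categorical variables by numerator, denominator and percent. SAP 7.5 reduces denominators for missing data. At stake is a named secondary objective that two analysts could report differently from the same data.

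**Working it through.** **The plan's own figures.** The documents give no figure for 1-year survival. Their ORR operating characteristics (11 then 18 subjects, continue at 2 or more responses, success at 4 or more) reproduce by exact binomial sums: stopping probability 0.6974 at 10% and 0.1130 at 30%, one-sided alpha 0.0875, power 0.8001. They do not depend on this point.

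**Inputs for the survival check.**
- Median survival 11.7 months, 95% CI 9.4–15.0 (Protocol 5.5.3, a prior phase 2 study in intermediate- to high-risk MDS). It is illustrative, not a planning value of this trial.
- Disease assessments about every 12 weeks (SAP 4.1): 12 × 7 / 30.4375 = 2.76 months.
- Follow-up to 12 months after accrual ends (SAP 4.1).
- Accrual of 12 months: assumed from the total of about 24 months in the Protocol synopsis, less 12 months of follow-up. Also run at 6 and 24 months.
- Median PFS of 3 and 6 months: assumed. Also run at 12.4 months, the median time to progression of complete responders in the same prior study.
- Enrollment-to-dose gap uniform from 0 to 0.25 months: assumed. Also run up to 0.92 months (28 days).

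**True value.** With exponential times, S(12) = 2^(−12/11.7) = 0.491.

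**Simulation.** 1,000,000 subjects per setting. Death and progression are drawn independently from exponential distributions, assessments run to the visit that detects progression, and there is no loss to follow-up. A subject with no post-baseline assessment is anchored at screening. The crude figure is 1 minus the proportion with a counted death.

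| Median survival / median PFS / accrual (months) | True S(12) | Crude, first-dose anchor | Crude, either anchor | Kaplan-Meier at 12, either anchor | Shortfall, either anchor (points) |
|---|---|---|---|---|---|
| 11.7 / 6 / 12 | 0.491 | 0.487 | 0.380 | 0.491 | 11.1 |
| 11.7 / 3 / 12 | 0.491 | 0.487 | 0.397 | 0.491 | 9.4 |
| 11.7 / 12.4 / 12 | 0.492 | 0.488 | 0.368 | 0.492 | 12.4 |
| 11.7 / 6 / 6 | 0.491 | 0.488 | 0.419 | 0.491 | 7.2 |
| 11.7 / 6 / 24 | 0.491 | 0.487 | 0.344 | 0.491 | 14.7 |
| 9.4 / 6 / 12 | 0.412 | 0.408 | 0.300 | 0.412 | 11.2 |
| 15.0 / 6 / 12 | 0.574 | 0.570 | 0.469 | 0.574 | 10.5 |
| 24 / 6 / 12 | 0.707 | 0.705 | 0.622 | 0.707 | 8.5 |

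**Where the shortfall comes from.** In the first row 1 − 0.380 = 0.620 of subjects have a counted death, and 17.9% of those deaths fall after month 12: 0.620 × 0.179 = 0.111. Removing them leaves 0.620 − 0.111 = 0.509 = 1 − 0.491, so the late deaths explain the whole gap. In a full cohort, 0.111 × 18 is about 2 subjects.

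**Why Kaplan-Meier at month 12 is unaffected.** The first dose is at or after enrollment, so every death within 12 months of enrollment is also within 12 months of the first dose and is admitted. Deaths after month 12 do not enter the estimate at month 12.

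**Time origin.** The mismatch between the enrollment clock and the first-dose window costs a crude rate 0.491 − 0.487 = 0.4 points, or 0.492 − 0.479 = 1.3 points with gaps up to 28 days.

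**PFS.** The text does not say whether the window limits only deaths or progressions as well, so no figure is given.

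**The case against.** Survival is defined as a time in months, the objective fixes the cut-off at 1 year, and SAP 7.5 speaks of censoring in survival analysis. All three point towards a time-to-event estimate read at 12 months, where the window does no harm. An analyst who saw a survival time of 20 months would hardly score that subject as not surviving 1 year. The shortfall also needs both anchors to apply; with the first-dose anchor alone it is 0.4 points. This stands, and it limits the point to a definition that permits a wrong figure. It does not remove the point: the documents neither name the estimator nor choose the anchor, and a subject with a recorded death outside the window is not a dropout under SAP 7.5.

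Three stronger inferences are tempting and are not supported:

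- **That the reported figure cannot be a 1-year survival rate.** It can, under either of the two benign readings above.
- **That the deaths the rule ignores bias the rate.** The first-dose anchor admits every death within 12 months of dosing, so each ignored death is later than that and is rightly absent from a 1-year rate.
- **That starting at enrollment is an error.** It is a conventional origin in a randomized study. Protocol 14.2 does equate inclusion with the consent date, but Protocol 8.1, 9.3 and 11.1 place enrollment and number assignment after eligibility is confirmed. A 28-day gap before dosing is therefore not established.

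Consequence is limited too. With at most 18 subjects per cohort, 9 of 18 alive has an exact 95% interval of about 26–74%.

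**Conclusion.** The point holds as a defect of definition. The last-assessment anchor serves no purpose in a 1-year survival rate, no rule chooses between the anchors, and no estimator is named. The harm is conditional. Tabulating deaths admitted under both anchors understates 1-year survival by about 9–11 points (38–40% against 49%) at median survival 11.7 months, median PFS 3–6 months and 12 months of accrual. At median PFS 6 months the gap runs from about 7 to 15 points as accrual goes from 6 to 24 months. These figures rest on exponential, independent event times and complete follow-up, and none of the medians is a planning value of the trial. On the first-dose anchor alone, or by Kaplan-Meier at 12 months, the bias is essentially nil.

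The endpoint is secondary and descriptive. Sample size, the stage 1 rule and the ORR decision are untouched. It is worth correcting before database lock because a stated rule, not just an omission, allows the wrong count.

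**What to change.** Amend SAP 9.2 and Protocol 12.2.1 together:

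1. Delete the 1-year window and both of its anchors from the survival and PFS definitions.
2. Define survival as the time from one stated origin to death from any cause, censored at the last date known alive. Enrollment/randomization or first dose are both acceptable; define the chosen date explicitly and use it for PFS as well.
3. Report both 1-year rates as Kaplan-Meier estimates at 12 months with 95% confidence intervals.
4. If the window was put into PFS to keep out deaths long after the last assessment, write that as a PFS censoring rule, as SAP 9.2 already does for duration of response.

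The cost is wording. The plan already collects dosing, assessment, progression and survival information, and no visit or sample size changes.
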